Appendix 4: Patients' Global Impression of Change (PGIC)

Subjects will complete the PGIC at Day 30 (\pm 5 days), Day 60 (\pm 5 days), Day 90 (\pm 5 days), Day 120 (\pm 5 days), Day 150 (\pm 5 days), Day 180 (\pm 5 days), Day 210 (\pm 7 days), Day 240 (\pm 7 days), Day 270 (\pm 7 days), Day 300 (\pm 7 days), Day 330 (\pm 7 days), Day 360 (\pm 7 days).

Patients' Global Impression of Change (PGIC) scale.

Name:	Date:	DOB:

Chief Complaint:

Since beginning treatment at this clinic, how would you describe the change (if any) in ACTIVITY LIMITATIONS, SYMPTOMS, EMOTIONS and OVERALL QUALITY OF LIFE, related to your painful condition? (tick ONE box).

No change (or condition has got worse)	0	1
Almost the same, hardly any change at all		2
A little better, but no noticeable change		3
Somewhat better, but the change has not made any real difference		4
Moderately better, and a slight but noticeable change		5
Better, and a definite improvement that has made a real and worthwhile difference	0	6
A great deal better, and a considerable improvement that has made all the difference		- 7

In a similar way, please circle the number below, that matches your degree of change since beginning care at this clinic:

Much Better				No Change					Much Worse	
0	1	2	3	4	5	6	7	8	9	10
Patient's sig	gnatur	e:					1	Date:		

Reference: Hurst H, Bolton J. Assessing the clinical significance of change scores recorded on subjective outcome measures. J Manipulative Physiol Ther 2004;27:26-35.

3. LIST OF ABBREVIATIONS

Abbreviation	Description
AE	adverse event
ASA	American Society of Anesthesiologists
ATC	anatomical therapeutic class
AUC	area under the curve
BMI	body mass index
CI	confidence interval
CLBP	chronic low back pain
CRF	case report form
d	day
EMA	European Medicines Agency
FDA	Food and Drug Administration
hr, h	hour
ICF	informed consent form
ICH	International Conference on Harmonisation
IRC	Independent Review Committee
LOCF	last observation carried forward
LSM	Least Squares Means
MedDRA	Medical Dictionary for Regulatory Activities
min	minutes
MPADSS	Modified Post Anesthesia Discharge Scoring System
NRS	Numerical Rating Scale
n	number of subjects
PO	oral
RCT	randomized controlled trial
RFA	radiofrequency ablation
SAE	serious adverse event
SAP	statistical analysis plan
SD	standard deviation
SE	standard error
SOC	standard of care
TEAE	treatment-emergent adverse event
TESAE	treatment-emergent serious adverse event
TLF	table, listings and figures
WHO	World Health Organization
WHO-DD	World Health Organization – Drug Dictionary
WOFC	worst-observation-carried-forward

4. INTRODUCTION

This Statistical Analysis Plan (SAP) describes the planned final analysis and reporting of the clinical study CRS-107 titled “A single-center, randomized, pilot study to assess iovera® lumbar medial branch cryoneurolysis vs lumbar radiofrequency ablation (RFA) for facet mediated chronic low back pain”.

The structure and content of this SAP provide sufficient detail to meet the requirements identified by the US Food and Drug Administration (FDA), European Medicines Agency (EMA), and International Conference on Harmonisation (ICH) of Technical Requirements for Registration of Pharmaceuticals for Human Use: Guidance on Statistical Principles in Clinical Trials (1998). All work planned and reported for this SAP will follow internationally accepted guidelines, published by the American Statistical Association (1999) and the Royal Statistical Society (1993), for statistical practice.

The purposes of this SAP are to:

- Outline the types of analyses and presentations of data that will form the basis for drawing conclusions to the study objectives and hypotheses as outlined in the protocol.
- Explain in detail how the data will be handled and analyzed, adhering to commonly accepted standards and practices for Good Statistical Practice.

The following documents related to clinical study Protocol CRS-107 were reviewed in preparation of this SAP:

- Protocol v1.0, issued 11 APR 2022.
- Amendment-1, issued 06 FEB 2023.
- AICH Guidance on Statistical Principles for Clinical Trials (E9).

The reader of this SAP is encouraged to also read the clinical protocol and other identified documents for details on the planned conduct of this study. Operational aspects related to the collection and timing of planned clinical assessments are not repeated in this SAP unless relevant to the planned analyses.

5. STUDY OBJECTIVES

5.1. Primary Objective

The primary objective of this study is to assess the safety and feasibility of iovera® lumbar medial branch cryoneurolysis vs. radiofrequency ablation (RFA) for facet-mediated chronic low back pain (CLBP).

5.2. Secondary Objectives

The secondary objectives of this study are to:

1. Evaluate safety outcomes (i.e., adverse device effects, serious adverse device effects, adverse events [AEs]) related to iovera^o treatment vs. RFA;
2. Evaluate clinical outcomes related to iovera^o vs. RFA treatment including pain, functional disability, and concomitant medication use (including opioids and analgesics);
3. Evaluate the treatment success and failure rate of iovera^o medial branch cryoneurolysis vs. RFA;
4. Evaluate subject satisfaction with pain management;
5. Identify subgroups of patients who are most and least likely to benefit from iovera^o medial branch cryoneurolysis for facet-mediated CLBP.

6. STUDY OVERVIEW

[figure not shown]
This is a single-center, randomized, pilot study in adult subjects with facet-mediated CLBP. Thirty (30) subjects are planned for initial enrollment and will be randomized 1:1 to receive iovera^o medial branch cryoneurolysis or radiofrequency ablation.

This study is designed to determine if a full efficacy RCT can be successfully conducted using the procedures and protocols described in the current pilot study protocol, or if protocol modifications are necessary before moving forward with a full efficacy RCT. Furthermore, the study will assess the feasibility of the outcome measurements employed, construct a foundation for sample size calculation, and the acceptability/practicality of conducting the full efficacy RCT.

Randomization to treatment groups according to the randomization assignment will be performed on the day of treatment. The treatment groups are:

- **Group 1:** subjects will receive iovera^o cryoneurolysis of the medial branch nerves
- **Group 2:** subjects will receive RFA of the medial branch nerves

Figure 1 Study Schema

7. DEFINITIONS

Diagnostic Medial Branch Block (MBB)

As part of the eligibility criteria, subjects must have undergone two successful diagnostic medial branch blocks consisting of two positive blocks with local anesthetic only (i.e., no steroids) under fluoroscopic guidance that results in at least 50% relief of primary (index) pain for the duration of the local anesthetic used.

Treatment-emergent Adverse Events

Treatment-emergent adverse events (TEAEs) are adverse events started on/after the start of iovera^o treatment.

Baseline

Baseline is defined as the last available measurement or assessment prior to the start of study treatment.

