9.6.1. Adverse Events

Adverse events will be coded using the Medical Dictionary for Regulatory Activities (MedDRA v 26.1) or more recent version.

A treatment related adverse event will be considered a TEAE if it starts on/after the time of study (iovera^o or RFA) treatment. If an AE has a partial onset date and time, the imputed start dates will be used to determine treatment-emergence (**Section 9.1.1.2**).

All summaries of AEs will include AEs that occur after the start of iovera^o treatment. Events that start prior to iovera^o treatment will be identified in listings only.

AEs will be summarized using subject incidence table. An overview of AEs will be presented. This table will include n (%) of subjects with:

- Any TEAE
 - Maximum severity: Mild
 - Maximum severity: Moderate
 - Maximum severity: Severe
- At least one related TEAE
- At least one serious TEAE
- Subjects discontinued due to a TEAE
- Serious treatment-emergent adverse events (TESAEs)
- Died on study.

Additionally, n (%) are calculated based on the number of unique subjects within each MedDRA category (e.g., preferred term) by treatment group. A subject reporting multiple events of the same category will be counted only once for that category. For summary purposes, AE relationship to the iovera^o or RFA will be grouped into “Unrelated” for “unrelated” or “unlikely related” and “Related” for “possible”, “probably”, or “definite”. For subjects with more than one event coded to the same PT, the subjects will be counted for the categories with the strongest relationship and the greatest severity. The following subject incidence tables will be presented:

- TEAEs by PT (Preferred Term) sorted by the decreasing order of subject incidence in the combined group
- TEAEs by SOC (System Organ Class) and PT sorted alphabetically
- TEAEs treatment-related by SOC and PT
- TEAEs by severity and by SOC and PT

- TESAEs by SOC and PT.

A data listing will be provided for all AEs. Included in the listing are the reported term, PT, SOC, TEAE and TESAE flag, study day when AE starts, duration, relationship to treatment(s), severity, action taken, outcome, and seriousness category.

Separate data listings will be provided for subjects who experience SAEs and die on study.

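### The SAP's adverse-event dating rules contradict each other: Section 7 and two sentences in 9.6.1 start the clock at iovera treatment only, while one sentence in 9.6.1 uses either treatment

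*SAP*

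**What the plan says.** Four sentences in the SAP set the start point for treatment-emergent adverse events (TEAEs) and for their reporting.

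- Section 7, the definition: "Treatment-emergent adverse events (TEAEs) are adverse events started on/after the start of iovera^o treatment".
- Section 9.6.1, the TEAE sentence: "A treatment related adverse event will be considered a TEAE if it starts on/after the time of study (iovera^o or RFA) treatment".
- Section 9.6.1, the summary sentence: "All summaries of AEs will include AEs that occur after the start of iovera^o treatment".
- Section 9.6.1, the listings-only sentence: "Events that start prior to iovera^o treatment will be identified in listings only".

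Other parts of the documents bear on what is meant:

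- The safety set in SAP Section 8 takes in everyone randomised and treated with either procedure.
- SAP 9.6 reports safety by treatment group and overall, with no testing.
- The protocol's Safety Endpoints paragraph makes TEAE incidence the safety endpoint and does not limit it to iovera.
- Safety of iovera against RFA is part of the primary objective (SAP 5.1).

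**The concern.** A subject who receives only RFA has no iovera start. Three of the four sentences therefore cannot be applied to that subject as written.

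The start point matters in both arms. The protocol collects adverse events from consent, which may be up to 30 days before treatment, so events before the procedure can occur in RFA subjects too. They have to be separated from events after it.

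A programmer working from the SAP must either apply a definition that does not work for the comparator, or depart from the written definition without a record. In the second case the definition printed in the report would not match the tables. This concerns the comparison that the primary objective asks for.

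**Working it through.** No power or sample-size formula applies. The only planned figure involved is the allocation in SAP Section 10: 30 subjects randomised 1:1, so 30 / 2 = 15 RFA subjects, as the SAP states. The rest is a comparison of the text.

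**The four rules side by side**

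| Rule | Start point | Events it is worded for | Usable for an RFA subject? |
|---|---|---|---|
| Section 7, definition | iovera | all | no |
| 9.6.1, TEAE sentence | iovera or RFA | treatment-related | yes, for related events |
| 9.6.1, summary sentence | iovera | all | no |
| 9.6.1, listings-only sentence | iovera | all | no |

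Three rules name iovera only and one names both procedures.

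**The rules applied to events in an RFA subject**

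1. *Judged related, starting after RFA.* The 9.6.1 TEAE sentence makes it a TEAE. The Section 7 definition cannot be evaluated. The summary sentence gives no start point.
2. *Judged unrelated, starting after RFA.* The 9.6.1 TEAE sentence is not worded for it. Only Section 7 speaks, and it names iovera. No written rule gives a usable start point.
3. *Starting between consent and RFA.* It should go to the listings only, but that sentence is tied to iovera treatment.

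**What the table list shows about intent**

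- Relationship is assessed to either procedure: "For summary purposes, AE relationship to the iovera^o or RFA will be grouped into" two classes, unrelated and related.
- The overview table has a row for any TEAE and a separate row, "At least one related TEAE". The separate row would be pointless if TEAEs were related events only.
- The incidence tables include both "TEAEs by SOC (System Organ Class) and PT sorted alphabetically" and "TEAEs treatment-related by SOC and PT", which again requires unrelated TEAEs.
- The preferred-term table is sorted by incidence in the combined group, so RFA events must be counted.
- The definition of Baseline, next to the TEAE definition in Section 7, already refers to study treatment and names neither arm.

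**A smaller mismatch in the same sentences.** Section 7 says *on/after*, the summary sentence says *after*, and the listings-only sentence says *prior to*. An event timed exactly at treatment start is a TEAE under Section 7 but falls under neither of those two 9.6.1 sentences. SAP 9.1.1.2 can create such ties, because it sets an onset of unknown year to the date and time of study treatment (if that is read as the start time).

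**The case against.** The strongest reply is that the SAP does state an RFA start point. The 9.6.1 TEAE sentence names both procedures, and it stands ahead of the two sentences quoted against it. Section 9.6.1 then refers to 9.1.1.2 for partial dates, where the unknown-year rule uses study treatment, which fits either arm. Nothing in the SAP ranks Section 7 above 9.6.1. With the both-arm safety set, by-group reporting and the combined-group sort order, a programmer is unlikely to produce an empty RFA column.

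Most of this stands. It rules out two stronger readings that a reader might infer:

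- *That the SAP gives RFA subjects no treatment-emergent start date at all, or that the RFA arm will be lost from the safety tables.* The 9.6.1 TEAE sentence gives one for related events, and the table list shows that both arms are meant.
- *That unrelated events are excluded from TEAEs.* The 9.6.1 TEAE sentence says *if*, not *only if*, and the separate related and all-TEAE tables show that unrelated events count.

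The reply does not remove the contradiction. The both-arm sentence is worded only for related events and sets no summary or listings-only rule, so the gap in cases 2 and 3 of the working remains.

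It is also fair to say that the *after* versus *on/after* mismatch has little practical force. Every planned incidence table is a TEAE or serious-TEAE table, so an event at treatment start would enter it under Section 7.

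**Conclusion.** The point holds as an internal contradiction that is wrong as written and should be corrected. Three of the four start-point rules name iovera only. They conflict with the fourth, with the safety set, with by-group safety reporting and with the protocol's TEAE endpoint. For the 15 planned RFA subjects, no usable start point is written for unrelated events or for the summary and listings-only rules.

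The consequence is limited. Intent is recoverable, safety is descriptive, and the design is not in question. The documents give no adverse-event rates, so the number of events that could be misclassified cannot be estimated. The conclusion rests on the wording alone and assumes that an RFA subject receives no iovera treatment.

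**What to change.** Change SAP wording in four sentences:

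1. In Section 7, and to the same effect in 9.6.1, define TEAEs as *AEs, regardless of relationship, that start on/after the start of study treatment (iovera or RFA)*.
2. In the 9.6.1 TEAE sentence, delete *treatment related*.
3. In the 9.6.1 summary sentence, replace *iovera treatment* with *study treatment (iovera or RFA)*, and change *after* to *on/after* to match Section 7.
4. In the 9.6.1 listings-only sentence, make the same replacement of *iovera treatment*.

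Replacing *first dose* with *study treatment* in 9.1.1.2 is optional tidying. The protocol describes a single procedure, so no imputed date changes.

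The documents do not settle which moment of the procedure counts as the start of treatment, and this correction does not depend on choosing one.

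The cost is a short SAP revision, with no change to the protocol or to data collection. The documents do not say whether programming has begun. If it has, the TEAE flag should be checked against the corrected definition.

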9.1.1.2. Adverse Event (AE) and Prior/Concomitant Medications

It is expected that the dates and times for AEs will be complete. For AEs with missing or partially missing start date/time, the following imputation rules will be applied for the determination of treatment-emergent status:

For partial start date/time:

- If the year is unknown, then the date will be assigned the date and time of study treatment.
- If the year is known to be different from the year of the first dose, then missing month and day will be imputed as the first month and first day of the month.
- If the year is known to be the year of the first dose,
 - a) If the month is unknown or is the same as the month of the first dose, then the missing month and day will be imputed by the month and day of the first dose.
 - b) If the month is known to be different from the month of the first dose, then the missing day is imputed as 01 (first day of the month).

The same missing data handling techniques will be used for prior/concomitant medications.

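### The SAP decides treatment-emergence by start date alone, so an AE that begins between consent and treatment, worsens after the procedure and stays under its original record is left out of the TEAE tables

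*SAP*

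**What the plan says.** Three places in the SAP bear on treatment-emergence, and all three look only at when an event began.

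- Section 7: "Treatment-emergent adverse events (TEAEs) are adverse events started on/after the start of iovera^o treatment".
- Section 9.1.1.2, on incomplete dates: "For AEs with missing or partially missing start date/time, the following imputation rules will be applied for the determination of treatment-emergent status". The rules that follow deal only with the start date.
- Section 9.6.1 tests whether the event starts on or after iovera or RFA treatment, and for partial dates adds that "the imputed start dates will be used to determine treatment-emergence".

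Section 9.6.1 then fixes the consequence. It says "All summaries of AEs will include AEs that occur after the start of" treatment, and events with an earlier start "treatment will be identified in listings only".

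The protocol starts AE collection when the consent form is signed and continues it to Day 360 (Collection and Assessment of Adverse Device Events and Adverse Drug Events). It allows up to 30 days between consent and the procedure (Duration of Subject Participation in Study). Its AE definition, under Adverse Drug Event Definitions, includes deterioration as well as new onset.

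**The concern.** The protocol and the SAP treat worsening differently. In the protocol, a deterioration after consent is an adverse event. In the SAP, worsening plays no part in deciding whether an event is treatment-emergent. An event that begins in the screening interval and becomes worse after the procedure falls between the two if the site updates the existing record and does not open a new one.

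Safety is part of the primary objective (SAP Section 5.1) and is summarised descriptively, without testing (Section 9.6). The incidence tables by arm are therefore the main safety summary. In this case, whether a post-procedure worsening is tabulated would depend on a data-entry habit that neither document states.

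The omission also runs against the SAP's own tendency to count when in doubt. An unknown onset year becomes the treatment date (Section 9.1.1.2). A missing severity becomes severe and a missing relationship becomes definite (Section 9.1.1.3).

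**Working it through.** The SAP states no figure to reproduce here, so the check is of the classification rule.

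**Can such an event arise?** Yes. Collection opens at consent and treatment may follow up to 30 days later, so events with a pre-treatment start can be on record.

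**How does the rule classify it?** Take treatment as time 0. The SAP rule is: start ≥ 0. The amended rule is: start ≥ 0, or worsening ≥ 0.

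| Example | Recorded start | SAP rule | Amended rule |
|---|---|---|---|
| Begins 10 days before, worsens 5 days after, one record kept | −10 | Listing only | TEAE |
| Same event, worsening entered as a new record | +5 | TEAE | TEAE |
| Begins 2 days after treatment | +2 | TEAE | TEAE |

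Only the first row differs. The gap therefore needs both a start in the screening interval and a single record.

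**Does either document settle which record is used?** No. The AE definition says what counts as an event, not how to enter it. Under Reporting of Serious Adverse Device Events and SAEs, the protocol refers to EDC entry instructions that are not part of the documents.

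**Would the listing reveal it?** Not necessarily. The items named in Section 9.6.1 include "TEAE and TESAE flag, study day when AE starts, duration, relationship to treatment(s), severity, action taken, outcome, and seriousness category". No date of worsening is named, so a reader would see the event but might not see that it worsened after the procedure.

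**What is one subject worth?** Inputs: 15 per arm and 30 in all (SAP Section 10), assuming all are treated.

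- Arm: 1/15 = 6.7 percentage points.
- Overall: 1/30 = 3.3 percentage points.
- Exact (Clopper-Pearson) 95% intervals: 0/15 gives 0 to 21.8%; 1/15 gives 0.2 to 31.9%. They overlap heavily.

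These are upper limits on the change per subject. The any-TEAE row moves only if the subject has no other TEAE through Day 360. A preferred-term row moves only if the subject has no other post-treatment record under that term.

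**The case against.** The strongest reply is that the protocol already supplies the rule. Its AE definition counts deterioration, and any relevant untoward change after consent, as an adverse event. On that reading the worsening is an event in its own right with its own onset, and the SAP's start-date test counts it. SAP Section 4 also refers the reader to the protocol and says that operational aspects of data collection are not repeated. This reading is reasonable, and if sites follow it the gap closes. But neither document requires a new record, so the outcome is not assured.

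Several further limits stand:

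- Worsening of a condition noted before consent is already an adverse event under the protocol's collection section. The same sentence also mentions change after study treatment, which might be read to cover the screening interval. However, the section ties pre-existing conditions to those noted before consent.
- Table 1 has medical and surgical history updated, and eligibility confirmed again, on Day 1. The subject must also be medically fit for treatment. This reduces the number of events still ongoing at treatment but does not exclude mild ones.
- Where a second record with the same preferred term exists, Section 9.6.1 handles it: "the subjects will be counted for the categories with the strongest relationship and the greatest severity".
- Serious events must be captured within 24 hours and followed by a full written summary in the EDC. In addition, "Separate data listings will be provided for subjects who experience SAEs and die on study".
- The device summary in Section 9.6.2 carries no start-date condition.

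A reader might infer that serious post-procedure worsening could go unnoticed. The capture and listing rules do not support that. At most, the event could be missing from the TESAE table. A reader might also take the length of the screening interval, relative to the whole collection period, as the chance of the problem. It is only a share of calendar time. It says nothing about how many events are ongoing at treatment, worsen afterwards and stay under one record.

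**Conclusion.** The point holds in a narrow form. By its stated rule, the SAP leaves out of the TEAE tables an event that begins between consent and treatment, worsens after the procedure and is kept under its original record. This rests on one condition that the documents leave open, namely that the worsening is not entered as a new record.

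The number of affected subjects cannot be estimated from the documents and may be zero. A single affected subject would not change a descriptive reading of either arm. The event is not lost, because the all-AE listing still shows it. The documents do not support a claim that worsening in general goes uncounted, or that the safety conclusions are at risk. This is a low-priority clarification, worth making because it is cheap and because the pilot's procedures are meant to inform a full trial (SAP Section 6).

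**What to change.** In SAP Sections 7 and 9.6.1, define a TEAE as an adverse event that starts, or worsens in severity, frequency or seriousness, on or after the start of study treatment (iovera or RFA). Limit the listings-only rule to pre-treatment events that did not worsen afterwards.

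An alternative is a data-entry convention: post-treatment worsening of a pre-treatment event is recorded as a new event, with the date of worsening as its onset. Either route is enough. Using both could flag two records for one worsening, which would leave subject counts unchanged but duplicate flags in the listing.

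Naming both treatments also settles a separate wording point, since Section 7 mentions only iovera while Section 9.6.1 in one place names both. That adds no weight to the present point.

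The cost is a short SAP edit and one check of screening-period adverse events before database lock, in about 30 subjects. The downside is a possibly slightly higher reported TEAE rate.
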